3.3 Proposed Primary and Secondary Analyses

- 1. To compare the efficacy of Vamousse Lice Defence Shampoo with that of The Control Shampoo and to test for superiority in the intention-to-treat population.
- 2. To compare Vamousse Lice Defence Shampoo with The Control Shampoo in terms of safety.
- 3. To compare the cosmetic acceptability of Vamousse Lice Defence Shampoo with The Control Shampoo.
- 4. To compare the efficacy of Vamousse Lice Defence Shampoo with that of the Control Shampoo in the per-protocol population.

3.4 Statistical Methods

Sample size determination

The study has been designed to detect superiority of the test product (Vamousse Lice Defence Shampoo) (the treated group) to the comparator product (The Control Shampoo) (the placebo group) in clinical use.

The primary analysis proposed (see **Analytical Methods** below) is a comparison of the efficacy of the products with the aim to detect for superiority of Vamousse Lice Defence Shampoo to The Control Shampoo in the prevention of spread of infestation in a close household. The primary parameter on which this will be based is the proportion of individuals with active infestation at Day 14 in each household.

Stratifications – 1: <3 children in a household versus ≥ 3 children in a household and 2: overt infestations on Day 0 = 1 Index Case versus > 1 Index Case.

The principal analysis will be a stratified Kruskal-Wallis test using the Fry-Lee Test[1].

Significance will be declared at a level of 5%, using a two-sided test for greater percentage of infected family members in the placebo group versus the treated group.

To work out the numbers required to treat the code for calculating the probability of rejecting using the Fry-Lee Test[1] was put into an R routine, with the results validated against results from the proprietary package RoeLee[2].

From previous studies it was estimated that the infection rate in untreated families would be about 0.7 with standard error 0.367. The treatment is intended to lower the rate by 30%, so the rate in the treated group should be about 0.4 with standard error 0.367.

For a given number of families in each arm a random set of rates was then simulated using these mean and standard errors, using the R routine pnormal, truncating the values so that values less than zero were given the value zero, and values greater than one were given the value one.

The values were then checked to see if they would reject on a two-sided test at the significance level of 5%.

This process was repeated 5000 times and the rate of rejection used to estimate the power of the test.

If the power of the test was less than the required power, in this case 90%, the number of observations was increased and the process repeated.

To deal with stratification, two extra variables were simulated in each run, the first with a probability of being positive set at 0.5, and the second set at 0.7. The result of the test was calculated allowing for these strata.

Starting from a default value of 30 families per group the following results were found:

Kruskal Wallis Analysis of Data Study Size calculations based upon 5000 replicates

Normal Distribution. Test of Mean2 - Mean1 (Std.Dev. known). 2-sided . Wilcoxon-Mann-Whitney Use Truncated Normal Distribution - x < 0 -> 0, x > 1 -> 1Stratify data, (Fry-Lee Test). Two strata vars, 1:prob of strata level 2 = 0.7 2:prob of strata level 2 = 0.5Sample Size 1 as a function of Power and Significance Level. H0: Mean 2 - Mean 1=0 H1: Mean 1=0.7 H1: Mean 2=0.4 Std.Deviation 1=0.367 Std.Deviation 2=0.367, Sample Size 2 / Sample Size 1=1

Significance Level

| - 9 | | | |
|--------|------------|--------|-------|
| Number | .001 | 0.01 | 0.05 |
| Pov | ver Requir | ed: 90 | |
| 30 | 19.24 | 49.50 | 74.86 |
| 31 | 22.46 | 52.30 | 76.48 |
| 32 | 23.66 | 55.14 | 78.36 |
| 33 | 25.38 | 56.24 | 79.72 |
| 34 | 28.10 | 58.80 | 81.88 |
| 35 | 29.62 | 61.04 | 82.66 |
| 36 | 30.62 | 62.12 | 83.74 |
| 37 | 34.30 | 65.80 | 85.58 |
| 38 | 36.32 | 66.50 | 85.74 |
| 39 | 38.36 | 68.88 | 87.64 |
| 40 | 39.66 | 70.90 | 88.74 |
| 41 | 41.42 | 72.34 | 89.68 |
| 42 | 44.18 | 74.44 | 90.56 |
| | | | |

Thus 42 families per group should be sufficient to give a 90% power to detect a difference at two-sided significance level of 5%. Experience from previous studies of this kind suggests that drop-outs are infrequent. As described in section 3.2, non-compliant households will be included in the ITT analysis with the last observation for drop outs or lost to follow up cases carried forward for analysis. Nevertheless, should any families drop out of the study, recruitment will continue until at least 84 families have completed the study.

References

Analytical methods

Analyses will be conducted based on both the "intention-to-treat" and the "per-protocol" populations and will initially use conventional analytical methods employed in earlier studies. Differences between the groups in baseline characteristics, safety, acceptability, and efficacy will be tested using Fisher's Exact test for yes/no variables and the Mann-Whitney U test for ranked variables. Where analysis shows important differences in baseline characteristics between the groups, Chi-Square and rank tests stratified for these characteristics may also be conducted.

The primary endpoint, the rate of family members infested at the end of the trial, will be analysed by the stratified Kruskal-Wallis Test (Fry-Lee Test). This will be stratified on family size (<3 children in a household versus ≥3 children in a household) and overt infestations on Day 0 (=1 Index Case versus >1 Index Case). Significance will be declared at a level of 5% on a two-side test of the rate being lower in the treated group versus the placebo group.

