1.1 Summary of the Study

Title: Prevention of infestation with *Pediculus humanus*

capitis in the family group using a pediculicidal shampoo: A prospective, randomised controlled

study.

Chief Investigator: [name]

Study Monitoring: Onorach Limited

Estimated Study Start: January 2022

Estimated Study Finish: March 2022

Participants: Eighty-four (84) participants (the Index Cases) with

evidence of an active head louse infestation and their Households as the unit of randomisation will be recruited

to the study. All Index Cases will be treated with

Vamousse Treatment Mousse. Forty-two (42) participants and their Households will be treated with Vamousse Lice Defence Shampoo and forty-two (42) with The Control Shampoo. All participants will use the randomly assigned shampoo for fourteen (14) days and will be assessed for active head lice infestation at the end of that time.

Type: Eligible children and adults

Products: Vamousse Lice Defence Shampoo and The Control

Shampoo.

Methods of Application:

Both preparations will be applied to wet hair, massaged into the scalp and left in the hair for 3 minutes and no more than 5 minutes before rinsing with water and towel-drying. (see Section 2.3.3.2).

Study Design:

Participants will be recruited into the study by household and randomised to receive either Vamousse Lice Defence Shampoo or The Control Shampoo.

Index cases will be assessed for presence of head lice at their day of recruitment (Day 0) in order to ensure that all participants have live lice present at the start of the study. Other family members who proactively complain of head lice infestation will be treated as though they are an index case. All index cases will be treated the same day with Vamousse Treatment Mousse following confirmation of their eligibility. A member of the Medical Entomology Centre (MEC) study team will apply the treatment. All members of the household will commence using Vamousse Lice Defence Shampoo on Day 0 and will continue to use the shampoo daily for fourteen (14) days.

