3.1.2 Efficacy

The primary outcome of the study is the proportion of individuals in each household with active head lice infestation at day 14.

Secondary objectives are:

To demonstrate the safety of Vamousse Lice Defence Shampoo in clinical use.

To demonstrate the acceptability of Vamousse Lice Defence Shampoo in daily use.

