3.2 Definition of Populations to be analysed

The Per-protocol Population:

Includes all randomised participants who complete the study and are treated and followed up strictly according to the study protocol. For the purposes of the per protocol analysis, a study participant will be deemed to be non-compliant if the shampoo is not applied for at least seven (7) days during the study period and/or is not applied for four (4) consecutive days.

"Intention-to-treat" Population:

Includes all participants who consented and were treated at least once. Premature terminations due to drop out, treatment failure, adverse events etc., are included.

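### Households are randomised, but the non-primary efficacy, safety and acceptability comparisons are assigned Fisher's exact and Mann-Whitney tests that ignore household clustering

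*Protocol*

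**What the plan says.** Protocol section 1.1 recruits index cases with "their Households as the unit of randomisation". Sections 1.4 and 2.3.1 also randomise by household. The primary outcome in section 3.1.2 is a household quantity, "the proportion of individuals in each household with active head lice infestation at day 14". Section 3.4 tests it with the Fry-Lee stratified rank test on household rates, stratified by number of children and by overt infestations on Day 0.

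For the other comparisons, the analytical methods in section 3.4 carry over techniques from earlier studies. The key sentence opens "Differences between the groups in baseline characteristics, safety, acceptability, and efficacy will be tested using" and goes on to name two methods: Fisher's exact test where the outcome is binary, and the Mann-Whitney test where it is ordered. Section 3.4 then allows further testing: "Where analysis shows important differences in baseline characteristics between the groups, Chi-Square and rank tests stratified for these characteristics may also be conducted".

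The intention-to-treat population in section 3.2 is defined by person: "Includes all participants who consented and were treated at least once". Section 3.3 lists safety and cosmetic acceptability as between-arm comparisons. For none of these does the protocol mention clustering, an intraclass correlation, a household summary or a cluster-adjusted method.

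**The concern.** Fisher's exact test and the Mann-Whitney U test both treat each observation as independent. Members of a household receive the same allocation, use bottles labelled by household (section 2.2.2) and are exposed to the same index case. The rationale in section 1.2 rests on spread among close family members, so correlation within households is a premise of the trial.

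Counting each person as a separate unit then understates the variance of the difference between arms. A person-level efficacy p-value could stand beside the valid household-level one and disagree with it, and the protocol gives no order of precedence. Between-arm tests of acceptability and adverse events could flag differences too often. Person-level baseline tests share the fault, and the differences they show may prompt further stratified tests chosen after the data are seen.

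**Working it through.** **Inputs from the protocol (section 3.4).** 42 households per arm; two-sided 5%; household infestation rates of 0.7 (control) and 0.4 (treated); spread 0.367, called a standard error in the text and a standard deviation in the program output. The power simulation draws normal values with this spread and then sets values below 0 to 0 and above 1 to 1.

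**Assumed input.** Household size is not stated. Inclusion criterion 5 (section 2.1.2) implies an index child, a sibling and an adult, so at least three residents. I use 3, 4 and 5 participants.

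**Step 1: reproduce the plan's figure.** Simulating clipped normal household rates (0.7 against 0.4, SD 0.367), with two random strata (probabilities 0.5 and 0.7) and an unweighted stratified rank-sum test, gives 91.0% power at 42 per arm (4,000 replicates). The protocol states 90.56%, so its inputs are read as it used them. Under the null, the stratified rank test on household rates (van Elteren weights) rejects 5.6% of the time. The household-level approach holds its level.

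**Step 2: clustering implied by the protocol's spread.** For household size m and rate p:

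- design effect DE = SD² × m / [p(1−p)]
- ICC = (DE − 1)/(m − 1)
- approximate type I error of an unadjusted test = 2[1 − Φ(1.96/√DE)]

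With m = 4 and 0.367² = 0.1347:

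- p = 0.7: DE = 0.1347 × 4 / 0.21 = 2.57; ICC = 1.57/3 = 0.52; type I error 22.1%
- p = 0.4: DE = 0.1347 × 4 / 0.24 = 2.24; ICC = 1.24/3 = 0.41; type I error 19.1%

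**Step 3: the other reading of 0.367.** If 0.367 is the SD before clipping, the clipped rates have mean 0.661 and SD 0.2934 (from 0.7), or mean 0.418 and SD 0.3064 (from 0.4). With m = 4, DE = 0.2934² × 4 / (0.661 × 0.339) = 1.54 and ICC = 0.54/3 = 0.18. The second pair gives the same two values.

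**Step 4: simulate Fisher's test on individuals.** Beta-binomial data, no treatment effect, 42 households per arm, 6,000 replicates. The middle rate is (0.7 + 0.4)/2 = 0.55.

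| Reading of 0.367 | Rate | 3 people | 4 people | 5 people |
|---|---|---|---|---|
| SD of observed rates | 0.70 | 13.9% | 19.5% | 25.2% |
| SD of observed rates | 0.55 | 10.2% | 16.5% | 21.5% |
| SD of observed rates | 0.40 | 10.7% | 17.2% | 23.2% |
| SD before clipping | 0.661 | 5.8% | 9.0% | 13.9% |
| SD before clipping | 0.418 | 5.3% | 9.8% | 14.9% |

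A separate run of 4,000 replicates gave 13.5 / 18.8 / 23.9% at 0.70 and 11.3 / 16.7 / 22.0% at 0.40. Treating the clipped value as each household's underlying risk gives 11 to 21%. Allowing for simulation error, the ranges are roughly 10 to 26% and 5 to 15%.

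**Step 5: safety and acceptability (ICC assumed).** For an adverse event in 5% of people, with four per household, Fisher's test rejects about 4% at ICC 0.05 and 5% at ICC 0.1, because its conservatism offsets the clustering. At ICC 0.2, for events in 5 to 10% of people, it rejects about 9% with four people and 11 to 12% with five. A ranked acceptability score lacks that conservatism. With four people, DE = 1 + 3 × ICC gives 1.15, 1.3 and 1.6 at ICC 0.05, 0.1 and 0.2, and the formula in Step 2 gives about 7%, 9% and 12%.

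**The case against.** The best defence is that section 3.4 never states the unit for the generic tests. Day 14 infestation is fixed as a household proportion with its own household-level test, and section 3.3 lists no separate person-level infestation endpoint. A Mann-Whitney test on household rates would be valid, and the program output in section 3.4 gives the household-level test that very name. This stands in part: the person-level unit is an inference. It is a strong one, because a household proportion is not a yes/no variable, the populations are defined by participant, and section 1.4 records an individual who becomes infested as a treatment failure.

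A reader might infer a fixed figure of about 20%. The protocol does not support one. It gives no household size, and its simulation clips the rates, which lowers the realised spread.

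A reader might also infer that both secondary objectives are tested too liberally. That is not established. Their ICC is unknown, and for uncommon events Fisher's test may stay at or below 5%. For safety the direction would in any case be more false alarms, which does not favour the sponsor.

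Finally, the baseline-driven tests are optional, are triggered by important rather than significant differences, and replace nothing. Infestation severity is recorded for the index case, so it is largely one value per household.

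**Conclusion.** The concern holds in a limited form. The protocol names tests for independent observations for variables recorded per participant, although households are randomised. This is specified text, so an analysis plan that follows it would inherit the problem.

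For a person-level infestation comparison, the true type I error at a nominal 5% is roughly 10 to 26% if 0.367 is the SD of observed household rates, or roughly 5 to 15% if it is the SD before clipping. Both ranges assume three to five participants per household. For safety and acceptability, inflation is possible but its size is unknown.

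It would be wrong to conclude that the superiority claim is compromised. That claim rests on the Fry-Lee test of household rates, which is unaffected. The point should be fixed, but it does not threaten the primary conclusion. The baseline testing is a minor, related matter.

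**What to change.** In section 3.4, state that every person-level comparison between arms will use a method that respects the household. Any of these would serve: household-level summaries with a rank test; GEE clustered on household with a small-sample correction; or a permutation test that reassigns households within the two stratification factors. State also that the Fry-Lee result is the only confirmatory efficacy test, so that no person-level p-value competes with it. Preferably, present baseline characteristics descriptively without significance tests.

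The cost is a change of wording and slightly more programming. Some secondary p-values will become less extreme. No extra data, visits or households are needed.

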3.5 Final Study Report

A clinical report, integrating the study design and the results will be prepared for the study and agreed by the Chief Investigator and the Study Managers. The Chief Investigator, the Clinical Research Manager, and representatives of Alliance Pharmaceuticals Ltd. will sign a copy of the final study report.

4 Administrative Procedures

4.1 Regulatory Documentation

Any required legislative procedures will be undertaken before the commencement of the study. The study will not proceed without granted written approval.

This study will be conducted according to the recommendations of ISO 14155:2020 Clinical Investigation of Medical Devices for Human Subjects – Good Clinical Practice and ICH E6(R2) – Guideline for Good Clinical Practice.

4.2 Ethics Committee Approval

This formulation of Vamousse shampoo has not been approved for use in the European Union. Ethics approval will be required for the study (see http://www.hra-decisiontools.org.uk/ethics/).

4.3 Informed Consent

This study will be conducted in accordance with the principles laid down in the Declaration of the World Medical Assembly of Helsinki, and subsequent revisions (see Appendix 1).

Each participant or parent/guardian (where the participant is not legally competent) will be requested to provide written informed consent after receiving written information and a verbal explanation of what the study involves. A copy of the Consent Form will be returned to the participant and/or parent/guardian.

The Investigator will retain the original of the Consent Form and will also complete a Declaration of Receipt of Consent Form to confirm that written informed consent was obtained. The Investigator shall arrange for the retention of participant identification codes for at least 25 years after the completion or discontinuation of the study.

The Information and Consent documentation will include a GDPR statement regarding the security of personally identifiable data.

4.4 Insurance Policy

Alliance Pharmaceuticals Ltd. confirms that this specific clinical study is protected by insurance cover which provides an indemnity to the Investigators and their co-workers, subject to the Policy terms, conditions and limitations and provided always that the study is conducted and the data as reported agree to the standards fixed by the protocol. Indemnity, in the event of negligent acts by investigators in the field, must be covered by the professional liability insurance of the institution employing them.

4.5 Compensation

Alliance Pharmaceuticals Ltd. maintains in force a "no fault" compensation insurance indemnity in accordance with the current version of the ABPI Guidelines on Clinical Trials: "Compensation for Medicine Induced Injury". In the event that the compensation on a "no fault basis" is unacceptable to the claimant, the Policy will, subject to its terms, conditions and limitations, respond to an action for legal liability arising out of this clinical study.

4.6 Investigator's Responsibilities

Good Clinical Practice

It is the responsibility of the Investigators to ensure that this study is carried out in accordance with this protocol in respect of ethical, legal and technical aspects and

conforming to ISO 14155:2020, Clinical Investigation of Medical Devices for Human Subjects – Good Clinical Practice and ICH E6(R2) – Good Clinical Practice. In this context, the Investigator shall arrange for the retention of participant identification codes for at least 25 years after completion or discontinuation of the study. Alliance Pharmaceuticals Ltd. will render all support necessary to assist the Investigator in discharging this responsibility.

Replacement of Principal Investigator

In the event of a Chief/Principal Investigator being unable to continue the study, another responsible person may be designated Investigator and documentation testifying to this will be submitted to the study monitor within 10 days. The new Investigator must be appropriately qualified and be approved by Alliance Pharmaceuticals Ltd. before the study can be continued.

Study Report

The Chief Investigator will submit a summary study report within approximately 4 weeks of completion of the study. This report will include:

- 1. Details of the investigative procedures involved.
- 2. The numbers of participants entered, completed, and withdrawn from the study.
- 3. Deviations from the study protocol on a general basis and for individual participants, with explanations.
- 4. Explanations for each participant withdrawn from the study.
- 5. Summary of the safety and tolerance data, including details of all Adverse Drug Events (ADE) including any follow-up. Case histories of all serious ADEs or ADEs leading to withdrawal should be provided.
- 6. Conclusions

4.7 Curriculum Vitae

In accordance with international standards, and Good Clinical Research Practice, a signed copy of the curriculum vitae of the Principal Investigators, Research Physician/Co-Investigator, and members of the MEC study team will be provided to Alliance Pharmaceuticals Ltd./Onorach Ltd. and kept in the Trial Master File.

4.8 Case Record Form

The Investigator is required to prepare and maintain adequate and accurate case records that have been approved by Alliance Pharmaceuticals Ltd. to record all observations and other data pertinent to the clinical study. All CRFs should be completed in their entirety in a neat, legible manner to ensure accurate interpretation of data. Black ballpoint pen should be used to ensure the clarity of reproduced copies. Any alterations or errors to the CRF should be crossed through once only and signed and dated by the person making the change, using black ballpoint pen.

The study monitor will examine the original CRFs at each monitoring visit and will approve them when the CRF is complete and any necessary amendments have been made. The Investigator will not sign the CRFs until the study monitor has approved them. The Investigator will retain the CRFs until completion of data collection when they will be given to the study monitor for transfer to Alliance Pharmaceuticals Ltd.

The Investigator will retain a copy together with other source data for his/her own files. The CPMP Guidelines on Good Clinical Practice for Trials in the European Community require that the Investigator shall arrange for the retention of the participant identification codes for at least 25 years after the completion or discontinuation of the study. Participant files and other source data shall also be kept for the maximum period permitted by the institution but not less than 25 years.

